6.4. Changes From Protocol-Specified Efficacy Analyses

No change from the protocol-specified efficacy analysis is planned.

7. SAFETY ANALYSES

Safety data will be summarized for the participants in the All B/F/TAF Safety Analysis Set for the all B/F/TAF analysis, unless specified otherwise. All safety data collected up to 30 days after permanent discontinuation of study drug B/F/TAF will be summarized by treatment group, unless specified otherwise. All safety data will be included in data listings.

For the all B/F/TAF analysis, the terms "study drug start date (ie, the first dose date)", "study drug stop date (ie, the last dose date)", and "baseline" in the text below refer to the first dose date, the last dose date, and baseline defined for the all B/F/TAF phase analysis; the term "study drug" in the text below refer to B/F/TAF.

7.1. Adverse Events and Deaths

7.1.1. Adverse Event Dictionary

Clinical and laboratory AEs will be coded using the current version of MedDRA. System organ class (SOC), high-level group term (HLGT), high-level term (HLT), preferred term (PT), and lowest-level term (LLT) will be provided in the AE dataset.

7.1.2. Adverse Event Severity

Adverse events are graded by the investigator as Grade 1 (mild), Grade 2 (moderate), Grade 3 (severe) or Grade 4 (life threatening) according to toxicity criteria specified in the protocol. The severity grade of events for which the investigator did not record severity will be left as "missing" for data listings.

7.1.3. Relationship of Adverse Events to Study Drug

Related AEs are those for which the investigator selected "Related" on the AE eCRF to the question of "Related to Study Treatment." Events for which the investigator did not record relationship to study drug will be considered related to study drug for summary purposes. However, by-participant data listings will show the relationship as missing.

7.1.4. Serious Adverse Events

Serious adverse events (SAEs) will be identified and captured as SAEs if AEs met the definitions of SAE specified in the study protocol. Serious adverse events captured and stored in the clinical database will be reconciled with the SAE database from the Gilead Patient Safety (PS) Department before data finalization.

7.1.5. Treatment-Emergent Adverse Events

7.1.5.1. Definition of Treatment-Emergent Adverse Events

Treatment-emergent adverse events (TEAEs) are defined as 1 or both of the following:

- Any AEs with an onset date on or after the study drug start date and no later than 30 days after permanent discontinuation of the study drug, or
- Any AEs leading to premature discontinuation of study drug.

For the all B/F/TAF analysis, the AE onset date will be compared with the first and last dose dates for the All B/F/TAF phase analysis.

7.1.5.2. Incomplete Dates

If the onset date of the AE is incomplete and the AE stop date is not prior to the first dosing date of study drug, then the month and year (or year alone if month is not recorded) of onset determine whether an AE is treatment emergent. The event is considered treatment emergent if both of the following 2 criteria are met:

- The month and year (or year) of the AE onset is the same as or after the month and year (or year) of the first dosing date of study drug, and
- The month and year (or year) of the AE onset is the same as or before the month and year (or year) of the date corresponding to 30 days after the date of the last dose of study drug

An AE with completely missing onset and stop dates, or with the onset date missing and a stop date marked as ongoing or on or after the first dosing date of study drug, will be considered to be treatment emergent. In addition, an AE with the onset date missing and incomplete stop date with the same or later month and year (or year alone if month is not recorded) as the first dosing date of study drug will be considered treatment emergent.

7.1.6. Summaries of Adverse Events and Death

The number and percentage of participants who experienced at least 1 TEAE will be provided and summarized by SOC, HLT, PT, and treatment group. For other AEs described below, summaries will be provided by SOC, PT, and treatment group using the All B/F/TAF Safety Analysis Set:

- Any Grade 2, 3, or 4 treatment-emergent AEs
- Any Grade 3 or 4 treatment-emergent AEs
- All treatment-emergent study drug-related AEs
- Any Grade 2, 3, or 4 treatment-emergent study drug-related AEs
- Any Grade 3 or 4 treatment-emergent study drug-related AEs
- All treatment-emergent SAEs
- All treatment-emergent study drug-related SAEs
- All treatment-emergent AEs that caused premature discontinuation from study drug

A brief, high-level summary of AEs described above will be provided by treatment group and by the number and percentage of participants who experienced the above AEs. Treatment-emergent deaths observed in the study will be also included in this summary.

Treatment-emergent death refers to deaths that occurred between the first dose date and the last dose date plus 30 days (inclusive).

Multiple events will be counted only once per participant in each summary. Adverse events will be summarized and listed first in alphabetic order of SOC and HLT within each SOC (if applicable), and then by PT in descending order of total frequency within each SOC. For summaries by severity grade, the most severe grade will be used for those AEs that occurred more than once in an individual participant during the study.

In addition to the above summary tables, all treatment-emergent AEs, Grade 3 or 4 treatment-emergent AEs, treatment-emergent study drug-related AEs, Grade 2, 3, or 4 treatment-emergent study drug-related AEs, and treatment-emergent SAEs will be summarized by PT only, in descending order of total frequency.

All treatment-emergent AEs by SOC and PT will be summarized by subgroups defined in Section 3.4.1.

In addition, data listings will be provided for the following:

- All AEs
- Grade 3 and 4 AEs
- SAEs
- Study Drug-Related SAEs
- Death report
- AEs leading to premature discontinuation of study drug

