3.4. Duration of Treatment and End of Study

Subjects will be treated for at least 96 weeks. Following the Screening and Day 1 visits, subjects will be required to return for study visits at Weeks 4, 8, and 12, and then every 12 weeks from Week 12 through Week 96. Once all subjects complete their Week 96 visit and Gilead completes the Week 96 analysis, all subjects will return to the clinic (preferably within 30 days) for an End of Blinded Treatment Visit. At the End of Blinded Treatment visit, if safety and efficacy of B/F/TAF FDC is demonstrated for the HIV-1 and HBV coinfecting subjects following review of unblinded data, subjects in a country where B/F/TAF FDC is not available will be given the option to receive B/F/TAF FDC in an open label (OL) extension phase until the product becomes accessible to subjects through an access program, or until Gilead Sciences elects to discontinue the study in that country, whichever occurs first.

- a Following the Day 1 visit, subjects will be required to return for study visits at Weeks 4, 8, 12, and then every 12 weeks through Week 96.
- b After Week 96, all subjects will continue to take their blinded study drug and attend visits every 12 weeks until the End of Blinded Treatment Visit.
- c Once the last subject completes their Week 96 visit and Gilead completes the Week 96 analysis, all subjects will return to the clinic (preferably within 30 days) for an End of Blinded Treatment Visit. At the End of Blinded Treatment Visit, if safety and efficacy of B/F/TAF FDC is demonstrated for the HIV-1 and HBV coinfecting subjects following review of unblinded data, subjects in a country where B/F/TAF FDC is not available will be given the option to receive B/F/TAF FDC in an open label extension or until the product becomes accessible to subjects through an access program, or until Gilead Sciences elects to discontinue the study in that country, whichever occurs first.
- d Subjects who complete the study through the End of Blinded Treatment Visit and do not continue on the open-label rollover extension phase will be required to return to the clinic 30 days after the completion of study drugs for a 30-Day Follow-Up Visit.

CCI [REDACTED]

[REDACTED]

[REDACTED]

CCI
[Redacted text block]

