1.2. Study Design

Design Configuration and Participant Population

Study GS-US-380-4458 is a randomized, double-blinded, multicenter, active-controlled study to evaluate the safety and efficacy of B/F/TAF FDC versus DTG + F/TDF FDC in treatment-naïve, HIV-1 and HBV co-infected adult participants.

Treatment Groups

Participants who provide written consent and meet all eligibility criteria will be randomized in a 1:1 ratio to one of the following 2 treatment groups:

- Treatment Group 1 (n=120): FDC of BIC 50 mg/FTC 200 mg/ TAF 25 mg + placebo to match DTG 50 mg + placebo to match FDC of FTC 200 mg/TDF 300 mg administered orally, once daily, without regard to food
- Treatment Group 2 (n=120): DTG 50 mg + FDC of FTC 200 mg/TDF 300 mg + placebo to match FDC of B/F/TAF administered orally, once daily, without regard to food

Key Eligibility Criteria

Participants must meet all of the following inclusion criteria to be eligible to participate in the study:

- HIV-1 co-infection:
 - 1) Must be HIV antiretroviral treatment naïve with plasma HIV-1 RNA ≥ 500 copies/mL at screening
 - 2) \leq 10 days of prior therapy with any antiretroviral agent, including lamivudine and entecavir, following a diagnosis of HIV-1 infection (except the use for PrEP or PEP, up to one month prior to screening)
 - 3) Screening genotype report must show sensitivity to FTC and TFV. This report will be provided by Gilead Sciences. Alternatively, if genotype results from a local laboratory obtained ≤ 90 days prior to screening visit date show sensitivity to these drugs, this genotype will be acceptable to fulfill this inclusion criterion in the event that the genotype obtained at screening is not yet available and all other inclusion/exclusion criteria have been confirmed
- HBV co-infection:
 - 4) Must be HBV treatment naïve (defined as < 12 weeks of oral antiviral treatment)
 - 5) Screening HBV DNA ≥ 2,000 IU/mL
- Estimated glomerular filtration rate (eGFR) ≥ 50 mL/min according to the Cockcroft-Gault (C-G) formula (at the screening visit)

Study Periods/Phases

After screening, eligible participants will be treated for at least 96 weeks during the blinded treatment phase. Following the Screening and Day 1 visits, participants will be required to return for study visits at Weeks 4, 8, 12 and every 12 weeks thereafter.

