Once all participants complete their Week 96 visit and Gilead completes the Week 96 analysis, all participants will return to the clinic (preferably within 30 days) for an End of Blinded Treatment Visit. At the End of Blinded Treatment Visit, if safety and efficacy of the B/F/TAF FDC is demonstrated for the HIV-1 and HBV coinfected participants following review of unblinded data, participants in a country where the B/F/TAF FDC is not available will be given the option to receive the B/F/TAF FDC in an open label (OL) extension phase for up to 48 Weeks or until the product becomes accessible to participants through an access program, or until Gilead Sciences elects to discontinue the study in that country, whichever occurs first.

All participants participating in the OL extension phase, without regard to their blinded treatment regimen, will return for study visits at Week 12 OL and every 12 weeks thereafter.

Participants who complete the study through the End of Blinded Treatment Visit and do not continue on the OL extension phase, will be required to return to the clinic 30 days after the End of Blinded Treatment Visit for a 30-Day Follow-Up Visit.

Treatment assignments will be provided to the investigators within 30 days of the last participant completing the End of Blinded Treatment Visit.

Schedule of Assessments

After screening procedures, eligible participants will be randomized 1:1 to Treatment Group 1 or Treatment Group 2 and treated for 96 weeks. Following the Day 1 visit, participants will be required to return for study visits at Weeks 4, 8, and 12, and then every 12 weeks from Week 12 through Week 96. After Week 96, all participants will continue to take their blinded study drugs and attend a study visit every 12 weeks until the End of Blinded Treatment Visit.

Laboratory analyses (serum chemistry, liver function tests, hematology, urinalysis, pregnancy testing [for females of childbearing potential]), will be performed at the Screening, Day 1, and all subsequent study visits. HIV-1 RNA and CD4 + cell count will be performed at Screening, Day 1, and all subsequent study visits. HIV-1 genotype (RT and PR) will be determined at screening. Plasma HBV DNA levels, HBV serology (HBsAg and reflex anti-HBs Ab, and HBeAg and reflex anti-HBe Ab) will be performed at Screening, Day 1, and every 12 weeks thereafter. Plasma HBV DNA will be monitored at all study visits.

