3.2. Participant Grouping

For analysis using the All Randomized Analysis Set, participants will be grouped by the randomized treatment (labeled as B/F/TAF vs. DTG + F/TDF).

For all analyses included in the all B/F/TAF analysis, participants will be grouped into the following 2 groups:

- B/F/TAF group: This group includes all participants who actually received B/F/TAF in the randomized phase of this study, regardless whether participants receive any B/F/TAF in the extension phase or not.
- DTG + F/TDF to B/F/TAF group: This group includes all participants who actually received DTG + F/TDF regimen in the randomized phase of this study and then receive at least 1 dose of B/F/TAF in the extension phase.

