7.2.2.2. Summaries of Laboratory Abnormalities

The following summaries (number and percentage of participants) for treatment-emergent laboratory abnormalities will be provided by lab test and treatment group; participants will be categorized according to the most severe postbaseline abnormality grade for a given lab test:

- Treatment-emergent laboratory abnormalities
- Treatment-emergent Grade 3 and 4 laboratory abnormalities
- Treatment-emergent Grade 2, 3 and 4 laboratory abnormalities

For all summaries of laboratory abnormalities, the denominator is the number of participants with any nonmissing postbaseline values up to 30 days after last dosing date.

A by-participant listing of all laboratory abnormalities and Grade 3 or 4 laboratory abnormalities will be provided by participant ID number and visit in chronological order.

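### The final adverse-event and graded-laboratory tables set crude percentages side by side for two groups with unequal B/F/TAF time at risk (nominally 144 against 48 weeks)

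*SAP*

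**What the plan says.** SAP 7.1.6 sets the form of the adverse-event tables: "The number and percentage of participants who experienced at least 1 TEAE will be provided and summarized by SOC, HLT, PT, and treatment group". The further summaries by grade, relatedness, seriousness and drug discontinuation follow the same pattern in the All B/F/TAF Safety Analysis Set. SAP 7.1.7.2 does the same for hepatic events. In SAP 7.2.2.2 participants are classified by their worst postbaseline grade, and "the denominator is the number of participants with any nonmissing postbaseline values up to 30 days after last dosing date". All these denominators count people, not time.

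SAP 3.2 defines the two columns. One holds everyone who actually took B/F/TAF in the randomized phase, whether or not they rolled over. The other holds those who "received DTG + F/TDF regimen in the randomized phase of this study and then receive at least 1 dose of B/F/TAF" in the extension. SAP 3.8.1 starts the clock at the first blinded dose for the first group. For the second it starts at the first open-label dose, with a new baseline.

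On duration, SAP 1.2 says "eligible participants will be treated for at least 96 weeks during the blinded treatment phase". It adds that "After Week 96, all participants will continue to take their blinded study drugs" until the End of Blinded Treatment Visit. Participants in countries without access may then be offered B/F/TAF "in an open label (OL) extension phase for up to 48 Weeks". Protocol 6.6.2 has the same limit. Protocol 3.4 does not: there B/F/TAF is given "in an open label (OL) extension phase until the product becomes accessible to subjects through an access program", or until the sponsor ends the study in that country. Protocol 6.12, footnote a of Protocol Appendix 3 and footnote a of SAP Appendix Table 2 also state no 48-week limit. SAP Tables 3-2, 3-4, 3-6 and 3-9 carry Week 96 windows for switchers.

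SAP section 3 bases all tables on All B/F/TAF data and rules out comparisons between the groups. SAP 4.2.1 tabulates exposure duration separately. No exposure-adjusted rate, time-to-first-event summary or common time window is planned for adverse events or graded laboratory abnormalities.

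**The concern.** The proportion of people with at least one event rises with the time they are watched. If one column covers two to four times as much B/F/TAF time as the other, the percentages will differ even when the underlying risk is the same. The column with less time will look better.

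The reverse error is also possible. If event rates really rose after the switch, the shorter follow-up could offset the rise, and the table would show no difference or even an apparent advantage. A reader of the final report has these two percentages next to each other and nothing in the same table to show that they cover different lengths of treatment.

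**Working it through.** **Inputs from the documents.** Blinded B/F/TAF time is at least 96 weeks (SAP 1.2). Open-label time is up to 48 weeks (SAP 1.2, Protocol 6.6.2). Events count up to 30 days after the last dose in both groups (SAP 7.1.5.1). As an example of a common outcome, any adverse event by Week 48 in the Phase 2 study's bictegravir arm was 55/65 = 84.6% (Protocol 1.2.3.3).

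**Inputs assumed.** Blinded time after Week 96, *x*: 0 to 48 weeks. Share of the B/F/TAF group that rolls over, *q*: 0 to 1. Neither is given. Early discontinuation is ignored, and open-label participants are taken to complete the full 48 weeks.

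**Step 1: the plan's own figure.** SAP 6.3.1 pairs Week 144 with OL Week 48. This reproduces as 96 + 48 = 144 weeks, and 144/48 = 3.0. With the 30-day tail (4.29 weeks) on both sides it is 148.29/52.29 = 2.84.

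**Step 2: range of the mean exposure ratio.** Ratio = (96 + *x* + 48*q*)/48.
- *x* = 0, *q* = 0: 96/48 = 2.0
- *x* = 0, *q* = 1: 144/48 = 3.0
- *x* = 48, *q* = 0: 144/48 = 3.0
- *x* = 48, *q* = 1: 192/48 = 4.0

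If the extension instead ran 96 weeks, the ratio would be (96 + *x* + 96*q*)/96, or 1.0 to 2.5 over the same range. An open-label period shorter than 48 weeks would raise the ratio.

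**Step 3: displayed percentages at equal constant hazard.** If *p* is the 48-week risk shown for switchers, the B/F/TAF group shows 1 − (1 − *p*)^ratio.

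| Switchers | B/F/TAF, ratio 2 | B/F/TAF, ratio 3 | B/F/TAF, ratio 4 |
|---|---|---|---|
| 1% | 2.0% | 3.0% | 3.9% |
| 5% | 9.8% | 14.3% | 18.5% |
| 10% | 19.0% | 27.1% | 34.4% |
| 20% | 36.0% | 48.8% | 59.0% |
| 50% | 75.0% | 87.5% | 93.8% |
| 84.6% | 97.6% | 99.6% | 99.9% |

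At ratio 3, the two percentages stand in a ratio of 2.71 for a 10% event, 1.75 for a 50% event and 1.18 for the 84.6% event.

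**Step 4: masking.** Suppose switching doubled the hazard of a 10% event. Switchers would show 1 − 0.9² = 19.0%, against 27.1% at exposure ratio 3 and 19.0% at ratio 2. The doubling would look like a reduction in the first case and disappear in the second.

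**Step 5: the same data per unit of time.** A 10% risk at 48 weeks is −ln(0.9)/48 × 52.18 × 100 = 11.45 first events per 100 participant-years. Under the same assumption this is identical in both groups.

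**The case against.** The strongest reply is that the plan compares nothing. The SAP disclaims between-group comparison for this analysis, the safety objective runs only through Week 96 (SAP 1.1), and the Week 96 analysis is already done (SAP 2.2.2). The groups are labelled differently and their exposure is tabulated. This limits the consequences, but the percentages still stand side by side, and the exposure table does not enter any of them.

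A second reply is that Appendix 7 item 20 of the SAP applies the treatment-emergent definition to each phase separately. That is so, but SAP section 3 confines tables to All B/F/TAF data and uses randomized-phase data for listings. No phase-specific adverse-event table is specified.

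A third reply is that constant hazard is doubtful here, and it has force. Protocol 1.6 expects hepatic flares early in treatment. The B/F/TAF column includes that treatment-naive start. Switchers arrive after at least 96 weeks on the comparator and are re-baselined, and people who stopped drug early cannot enter the extension (Protocol 6.6.2). Part of any gap would therefore reflect phase and selection. Person-time rates alone could mislead in the other direction, by spreading early events over long follow-up.

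Three stronger readings are tempting, and the documents do not support them:
- A reader might infer that exposure differs three-fold by design. Three is only the nominal 144/48, and it depends on unknown rollover and on a cap that is stated inconsistently.
- A reader might take a 192-week exposure, and so a ratio of 4, as planned. No document gives it. It arises only with 48 assumed extra blinded weeks and full rollover.
- A reader might infer that these tables are the sole account of safety after the switch. By-visit summaries of laboratory values (SAP 7.2.1), liver tests (7.2.4), creatinine and eGFR (7.2.6.1) and vital signs and weight (7.3) are aligned on B/F/TAF time, and adverse events are also listed.

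**Conclusion.** The point holds for the descriptive event-incidence tables: adverse events, hepatic events and graded laboratory abnormalities. Their two columns cover B/F/TAF times in a nominal ratio of 3.0. The range is about 2 to 4 under the 48-week cap with 0 to 48 assumed blinded weeks after Week 96, and lower if the extension ran longer. The passages with and without the cap must be reconciled before the size can be fixed.

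The distortion is largest for events of middling frequency. It is small in absolute terms for rare events (1% against 3.0% at ratio 3) and small in relative terms for near-universal ones. These figures assume equal constant hazard and no early discontinuation, so they illustrate rather than predict. No primary or secondary conclusion depends on these tables. This is a worthwhile, inexpensive improvement to the safety display, not a flaw in the trial's inference.

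**What to change.** For the adverse-event overview, serious adverse events, events leading to discontinuation, hepatic events and Grade 3–4 laboratory abnormalities:

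1. Add a column for the B/F/TAF group's events during the open-label extension, with participants treated in that phase as the denominator, so that it can be read beside the switchers over the same phase. The rule in Appendix 7 item 20 already assigns adverse events to phases. For laboratory grades, state the baseline: Appendix 7 item 12 defines only the first randomized dose and the first B/F/TAF dose, which coincide for this group.
2. As a supplement, report participants with a first event per 100 participant-years at risk in each column.
3. Add a footnote giving each column's person-time, and stating that the groups differ in treatment history and selection and that the columns are descriptive.
4. Reconcile the statements on the length of the extension across the protocol and SAP.

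The cost is programming, since dose and onset dates are already collected, and wider tables. The rate assumes a roughly constant hazard, so it should not stand alone. If the SAP is not reopened, SAP section 1 already provides for documenting later changes in the clinical study report.
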